2.5.2 Statistical hypothesis, model, and method of analysis

The primary objective of the study is to assess the anti-tumor activity of the three treatment arms LAG525 + spartalizumab, LAG525 + spartalizumab + carboplatin and LAG525 + carboplatin, in subjects with advanced TNBC in first or second line of therapy, as measured by ORR per investigator's assessment according to RECIST v1.1. ORR based on RECIST1.1 will be calculated based on the FAS and according to the treatment group assigned at randomization following the Intent-To-Treat (ITT) principle.

In a randomized phase III study of carboplatin compared to docetaxel for subjects with metastatic or recurrent locally advanced triple negative breast cancer or *BRCAl/2* breast cancer, including 188 subjects randomized to carboplatin, the ORR with carboplatin in first line was 31.4% [Tutt et al 2014]. In the phase II clinical trial of platinum monotherapy in metastatic TNBC, with 86 subjects treated by carboplatin or cisplatin in first (69 subjects) or second line (17 subjects) the ORR was 25.6%. Specifically in second line, the ORR with cisplatin alone (9 subjects) was 22.2% and no subject responded in second line out of the 8 subjects treated by carboplatin [Isakoff et al 2015]. Based on cisplatin response rate in second line and considering that differences in population treated by the two drugs may explain the lower response rate observed with carboplatin, the ORR with carboplatin in second line is assumed around 20%.

Hence, based on those published results and assuming a similar proportion of subjects enrolled in first line and second line of therapy, the response rate with single agent carboplatin in subjects with advanced TNBC in 1st and 2nd line overall is expected to be 25%. A 10% absolute improvement in the response rate to 35% is considered a minimum clinically meaningful improvement in this study population. Therefore, proof of preliminary efficacy in each treatment group will be declared if both of the following conditions are met:

- the mean of the posterior distribution of ORR is at least 35%

and

- the posterior probability that the ORR is \geq 25% is at least 0.9

The posterior distribution of ORR will be derived from the prior distribution and all available data from the subjects included in the FAS. A minimally informative unimodal Beta prior [Neuenschwander et al 2008] will be used for ORR in each arm (see [Appendix 2 of study protocol](#) for further details). All available data from the subjects included in the FAS will be used to derive posterior distribution of ORR by treatment arm.

The study will be positive if the proof of preliminary efficacy is declared for any treatment group.

ORR will be summarized using descriptive statistics (N, %) by treatment group along with the two-sided exact binomial 95% confidence interval [[Clopper and Pearson 1934](#)].

2.5.3 Handling of missing values/censoring/discontinuations

Subjects with unknown or missing BOR as per RECIST 1.1 will be counted as failures. If there is no baseline tumor assessment, all post-baseline overall lesion responses are expected to be ‘Unknown’. If no valid post-baseline tumor assessments are available, the best overall response must be “Unknown” unless progression is reported. If a complete response is not confirmed, the best overall response must be “Unknown” unless it occurs after the first 5 weeks (stable disease), or confirmed partial response or progression is reported. If a partial response is not confirmed, the best overall response must be “Unknown” unless it occurs after the first 5 weeks (stable disease) or progression is reported. For the computation of ORR, these subjects with unknown BOR will be included in the FAS and will be counted as ‘failures’.

Only tumor assessments performed on or before the start of a new antineoplastic treatment other than study drug(s) (not considering palliative radiotherapy) will be considered in the assessment of BOR.

2.5.4 Supportive analyses

A sensitivity analysis considering subjects with unconfirmed PR or CR as responders may be performed if large delayed treatment effect is observed (i.e. with PR or CR at the last assessment prior to the cut-off date and ongoing in efficacy follow-up).

Timing of all tumor assessments will be depicted graphically for investigators’ review of tumor assessments and displayed by treatment arm.

Subgroup analysis for ORR

The primary endpoint of ORR will be summarized using descriptive statistics (N, %) for the subgroups specified in [Section 2.2.1](#) based on the primary analysis source (i.e., investigator assessment) and the same conventions as for the primary analysis.

Reasons for “Unknown” BOR

Subjects with ‘unknown’ BOR will be summarized by reason for having unknown status. The following reasons will be used:

- No valid post-baseline assessment

- All post-baseline assessments have overall lesion response UNK
- New anti-neoplastic therapy started before first post-baseline assessment
- SD too early
- PD too late

Note 1: A SD is considered as “SD too early” if the SD is documented within first 5 weeks after randomization date (i.e. until Day 35 included).

Note 2: A PD is considered as “PD too late” if the first documentation of PD is recorded more than 13 weeks after randomization date (i.e. from Day 92 included) with no qualifying CR, PR or SD in between.

Note 3: Special (and rare) cases where BOR is “unknown” due to both too early SD and too late PD will be classified as “SD too early”.

Waterfall plot to depict anti-tumor activity

Waterfall graphs will be used to depict the anti-tumor activity. These plots will display the best percentage change from baseline in the sum of diameters of all target lesions for each subject. Only subjects with measurable disease at baseline will be included in the waterfall graphs. Special consideration is needed for assessments where the target lesion response is CR, PR or SD, but the appearance of a new lesion or a worsening of non-target lesions results in an overall lesion response of PD. As a conservative approach, such assessments will not be considered for display as bars in the graph, since the percentage change in the sum of diameters of target lesions reflects the non-PD target lesion response, but the overall lesion response is PD. A subject with only such assessments will be represented by a special symbol (e.g. ★) in the waterfall graph. Assessments with “unknown” target lesion response and assessments with unknown overall response will be excluded from the waterfall plots. Subjects without any valid assessments will be completely excluded from the graphs.

The total number of subjects displayed in the graph will be shown and this number will be used as the denominator for calculating the percentages of subjects with tumor shrinkage and tumor growth. Footnote will explain the reason for excluding some subjects (due to absence of any valid assessment).

All possible assessment scenarios are described in [Table 2-11](#).

Table 2-9 Inclusion/exclusion of assessments used in waterfall graph

case	Criteria for inclusion/exclusion			Possible sources of contradictions	
	Target response	Overall lesion response	Include in waterfall?	Non-target response	New lesion?
1	CR/PR/SD	PD	Yes but as ★ only	PD	any
2	CR/PR/SD	PD	Yes but as ★ only	any	Yes
3	UNK	UNK or PD	No	any	any
4	CR/PR/SD	UNK	No	UNK	No
5	CR/PR/SD	CR/PR/SD	Yes as a bar	SD/IR	No
6	PD	PD	Yes as a bar	any	any

Percentage change from baseline in the sum of diameters of all target lesions over the time will be displayed for individual subjects.

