5.1 Inclusion criteria

Participants eligible for inclusion in this study must meet all of the following criteria:

- 1. Patient is an adult \geq 18 years old at the time of informed consent, and has signed informed consent before any trial related activities and according to local guidelines
- 2. Patient has advanced (loco-regionally recurrent not amenable to curative therapy or metastatic) breast cancer.
- 3. Patient has an Eastern Cooperative Oncology Group (ECOG) performance status of 0 or 1.
- 4. Patient has adequate bone marrow and organ function as defined by the following laboratory values (as assessed by central laboratory for eligibility):
 - Absolute neutrophil count $\geq 1.5 \times 10^9/L$
 - Platelets $> 100 \times 10^9/L$
 - Hemoglobin $\geq 9.0 \text{ g/dL}$
 - Creatinine clearance (calculated using Cockcroft-Gault formula, or measured) ≥ 40 mL/min
 - Alanine aminotransferase (ALT) < 3 x ULN, except for patients that have tumor involvement of the liver, who may only be included if ALT ≤5.0 x ULN who are excluded if ALT > 5 x ULN
 - Aspartate aminotransferase (AST) < 3 x ULN, except for patients that have tumor involvement of the liver, who may only be included if AST ≤5.0 x ULN who are excluded if AST > 5 x ULN
 - Total serum bilirubin < 1.5 ULN; or total bilirubin ≤ 3.0 × ULN with direct bilirubin within normal range of the central laboratory in patients with well documented Gilbert's Syndrome
- 5. Patient must have measurable disease, i.e., at least one measurable lesion as per RECIST 1.1 criteria (Tumor lesions previously irradiated or subjected to other loco-regional therapy will only be considered measurable if disease progression at the treated site after completion of therapy is clearly documented).
- 6. Patient progressed after adjuvant or 1 prior systemic treatment in the advanced setting. Patients with *de novo* metastatic disease are eligible if they received 1 prior line of therapy.
- 7. Patient must have received prior systemic treatment that included taxane-based chemotherapy for adjuvant or metastatic disease.
- 8. Patient must have a site of disease amenable to biopsy, and must be willing to undergo a new tumor biopsy at screening and during therapy on this study, the latter if medically feasible. Patients with an available archival tumor tissue do not need to perform a tumor biopsy at screening if patient has not received anti-cancer therapy since the biopsy was taken.

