Additionally, ORR will be summarized by treatment group along with the two-sided exact binomial 95% confidence interval Clopper CJ and Pearson 1934.

Waterfall graphs, which display the best percentage change from baseline in the sum of diameters of all target lesions for each participant with measurable disease at baseline, will be used to depict the anti-tumor activity of each treatment group.

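### SAP Table 2-9 counts one kind of RECIST progressor in the waterfall percentages and drops another, and dropping that subset can only raise the shrinkage percentage

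*SAP*

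**What the plan says.** **Population.** Protocol 12.4.2 plans waterfall graphs of the best percentage change in the sum of target-lesion diameters "for each participant with measurable disease at baseline, will be used to depict the anti-tumor activity of each treatment group". SAP 2.5.4 starts from the same set: "Only subjects with measurable disease at baseline will be included in the waterfall graphs". Protocol 5.1 makes this an entry criterion ("Patient must have measurable disease, i.e., at least one measurable lesion as per RECIST 1.1 criteria"), so the set should be nearly the whole FAS.

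**Which assessments count.** The table headed Table 2-9 (cited in the text as Table 2-11) sorts assessments by target response and overall lesion response:

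- Cases 1 and 2: target CR, PR or SD, but overall PD through non-target worsening or a new lesion. No bar is drawn, but "A subject with only such assessments will be represented by a special symbol".
- Case 3: target unknown, overall unknown or PD. Not included.
- Case 4: target CR, PR or SD, overall unknown. Not included.
- Cases 5 and 6: target and overall response agree. Shown as a bar.

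The text matches the table. Assessments with an unknown "target lesion response and assessments with unknown overall response will be excluded from the waterfall plots".

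**Participants and denominator.** "Subjects without any valid assessments will be completely excluded from the graphs". The number displayed is printed on the graph, and "this number will be used as the denominator for calculating the percentages of subjects with tumor shrinkage and tumor growth". On disclosure: "Footnote will explain the reason for excluding some subjects (due to absence of any valid assessment").

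**The concern.** Two participants can have the same RECIST outcome, overall progression, and be handled in opposite ways. If the target lesions were measured and had not progressed, the participant stays on the graph as a star and in the denominator. If even one target lesion was not assessed, so that target response is unknown, and there is no other valid assessment, the participant leaves both the graph and the denominator. The primary analysis does not do this: ORR is computed on the FAS, and such a participant is a non-responder there.

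At stake is one descriptive figure per arm, the percentage with tumour shrinkage. A reader who sets it beside ORR may assume that both rest on the same participants. The planned footnote gives lack of a valid assessment as the reason for exclusion, so it would not show that some of those excluded had documented progression.

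**Working it through.** The documents state no waterfall percentage and no count of excluded participants, so there is no plan figure to reproduce. The check has four steps.

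**1. Can case 3 with overall PD occur?** Yes. In Protocol Appendix 3, Table 16-4 gives overall PD for any target status when there is a new lesion or non-target progression. Table 16-2 makes the target response unknown when progression has not been documented in the targets and one or more of them was not assessed, or was assessed by a different method.

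**2. Same overall outcome, different handling.**

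| Participant's only assessments | On graph | In denominator | ORR (FAS) |
|---|---|---|---|
| Overall PD, targets measured and not PD (cases 1-2) | Star | Yes | Non-responder |
| Overall PD, target response unknown (case 3) | No | No | Non-responder |

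**3. Effect of dropping case-3 progressors.** Let M be the participants with measurable disease, s those plotted with shrinkage, and k the case-3 progressors dropped. A dropped progressor has no measured change and so cannot belong to s.

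- Displayed figure: s/(M − k)
- Full-set figure: s/M
- Ratio: M/(M − k), which exceeds 1 whenever k > 0

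The growth percentage has the same denominator and rises by the same factor.

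M is set to arm sizes in the Amendment 4 summary (20 randomized in Arm 1, 34 in each of Arms 2 and 3), taking all as having measurable disease. Both s (half the arm) and k are assumptions.

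| k | M = 34, s = 17 | M = 20, s = 10 |
|---|---|---|
| 0 | 17/34 = 50.0% | 10/20 = 50.0% |
| 1 | 17/33 = 51.5% | 10/19 = 52.6% |
| 2 | 17/32 = 53.1% | 10/18 = 55.6% |
| 3 | 17/31 = 54.8% | 10/17 = 58.8% |
| 5 | 17/29 = 58.6% | 10/15 = 66.7% |

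The excess for k = 1 to 5 is 1.5 to 8.6 points at M = 34 and 2.6 to 16.7 points at M = 20.

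**4. Effect of all exclusions together.** Step 3 cannot be extended to the whole rule. A case-4 participant has measured targets that may have shrunk, and is lost from numerator and denominator alike. Assume 34 eligible, 4 dropped for any reason, and 16 of the 30 plotted with shrinkage, so the displayed figure is 16/30 = 53.3%.

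- None of the 4 had shrinkage: 16/34 = 47.1%. The display is too high.
- Two were case 4 with shrinkage: 18/34 = 52.9%. The two figures nearly agree.
- Three were case 4 with shrinkage: 19/34 = 55.9%. The display is too low.

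**The case against.** The strongest reply is that a waterfall shows measured change. A participant with no measured change has no bar, and using the plotted number as denominator, openly stated, is a common convention. The SAP prints that number, adds a footnote on exclusions, and separately tabulates unknown best overall response by reason. This stands as far as it goes: a reader can see that the plotted number is below the arm size. It does not explain why the stars, which also have no bar, are counted while case-3 progressors are not. Nor does the footnote's stated reason identify them.

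It is also fair to say that the case is probably uncommon. Protocol 8.3.1 requires chest, abdomen and pelvis imaging at each on-treatment assessment and a complete imaging assessment once suspected progression is confirmed, and one valid assessment keeps a participant on the graph. That limits the size of the effect but does not remove the inconsistency.

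Three stronger readings are tempting, and the documents do not support them:

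- **That the rule as a whole removes progressors and inflates shrinkage.** The exclusions also cover participants with no post-baseline scan, those with only unknown responses, and case 4. Step 4 shows that the net direction can go either way.
- **That the rule defeats the SAP's own conservative aim.** The SAP uses that description only for withholding bars in cases 1 and 2. It does not apply it to case 3 or to the denominator.
- **That a main efficacy figure is affected.** The SAP places the waterfall under supportive analyses. The secondary efficacy endpoints are DOR, TTR, PFS, CBR and OS, and Protocol 12.4.2 describes the graph without any shrinkage percentage.

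**Conclusion.** The point holds in a narrow form. Table 2-9 handles two kinds of documented progressor inconsistently, and for the kind it drops, the shrinkage percentage can only go up. With assumed values of 34 eligible and 17 with shrinkage, dropping 1 to 5 such participants moves the figure from 50.0% to between 51.5% and 58.6%. If none exists, nothing changes. This rests on assumed numbers of dropped and shrinking participants, on a half-arm shrinkage rate, and on every randomized participant having measurable disease. The net bias of the displayed percentage over all exclusions cannot be signed from the documents.

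The consequence is confined to a descriptive display. ORR and the proof-of-preliminary-efficacy rule use the FAS, with unknown best overall response counted as failure, and are untouched. Amendment 4 reports that the primary efficacy analysis was done at a cut-off of 27-Feb-2020 and that no arm met the criteria. The change is therefore worthwhile but minor, and matters only if the figure is re-run or reported further.

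**What to change.** 1. Split case 3 of Table 2-9. Unknown target response with overall PD gets a symbol, as in cases 1 and 2, and is counted. Unknown target with unknown overall response stays off the graph.
2. Calculate the shrinkage and growth percentages on FAS participants with measurable disease at baseline, the set named in Protocol 12.4.2, or print that percentage beside the one based on the displayed number.
3. Split the exclusion footnote into counts of participants with only unknown assessments (including case 4) and participants with no post-baseline scan.

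This costs one table row, a denominator definition and a footnote, and needs no new data. The descriptive percentage becomes slightly less favourable. On the fixed denominator, case-4 participants count without a bar even if their targets shrank, which is why their number belongs in the footnote. Because the primary analysis has already been run, any re-issued figure should state that the denominator was changed afterwards.

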2.6 Analysis of the key secondary objective

Not applicable

2.7 Analysis of secondary efficacy objective(s)

The secondary efficacy objectives are:

- To assess the efficacy of the three treatment arms with respect to Duration of response (DOR), Time to response (TTR), Progression Free Survival (PFS) and Clinical benefit rate (CBR) per investigator's assessment according to RECIST v1.1
- To assess Overall Survival for each treatment arm

2.7.1 Secondary endpoints

Duration of response (DOR)

Duration of response only applies to subjects whose best overall response is complete response (CR) or partial response (PR) according to RECIST 1.1 based on local investigators' review of tumor assessment data. The start date is the date of first documented response of CR or PR (i.e., the start date of response, not the date when response was confirmed), and the end date is defined as the date of the first documented progression or death due to underlying cancer. Subjects continuing without progression or death due to underlying cancer will be censored at the date of their last adequate tumor assessment using the censoring rule described for PFS analysis (see [Section 2.7.3](#)).

Time to response (TTR)

Time to response (CR or PR) is the time from date of randomization to first documented response of CR or PR (which must be confirmed subsequently using local investigators' review of tumor assessment data and according to RECIST 1.1). The start date is the date of first documented response of CR or PR (i.e., the start date of response, not the date when response was confirmed).

All subjects in the FAS will be included in the time to response calculation. Subjects who did not achieve a confirmed PR or CR will be censored at:

- the maximum follow-up time (i.e. FSFV - LSLV used for the analysis) for subjects who had a PFS event (i.e. either progressed or died due to any cause);
- the last adequate tumor assessment date for all other subjects.

Progression-Free Survival (PFS)

PFS is defined as time from date of randomization to the date of event defined as the first documented progression or death due to any cause. PFS will be assessed via local review of tumor assessments according to RECIST 1.1 (see [Appendix 3 of study protocol](#) for further details). The analysis will be based on FAS and will include all data observed up-to the cut-off

date. PFS will be censored at the date of the last adequate tumor assessment if no PFS event is observed prior to the analysis cut-off date or before the start of the new anticancer therapy date, whichever is earlier (see [Section 2.7.3](#) for additional details regarding censoring rules and determination of date of last adequate tumor assessment).

Discontinuation due to disease progression (collected on the ‘Treatment disposition’ and ‘Post treatment follow up disposition’ eCRF pages) without supporting objective evidence satisfying progression criteria per RECIST 1.1 will not be considered disease progression for PFS derivation. Clinical deterioration will not be considered as a qualifying event for progression.

Clinical benefit rate (CBR)

CBR is defined as the proportion of subjects with a best overall response (BOR) of confirmed CR or PR, or SD lasting 24 weeks or longer, according to RECIST 1.1 criteria. A subject will be considered to have SD for 24 weeks or longer if a SD response is recorded at (24-1) weeks or later from randomization, allowing for the ± 1 week visit window for tumor assessments. CBR will be calculated using the FAS based on the investigators’ tumor assessments.

Overall Survival (OS)

Overall Survival is defined as the time from date of randomization to date of death due to any cause. All deaths occurring on or before the cut-off date in the FAS will be used in the OS analysis. If a subject is not known to have died, then OS will be censored at the latest date the subject was known to be alive (on or before the cut-off date).

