12.5.1 Efficacy and/or Pharmacodynamic endpoint(s)

Clinical benefit rate (CBR) is defined as the proportion of participants with a best overall response of complete response (CR) or partial response (PR) or an overall lesion response of stable disease (SD), lasting for a duration of at least 24 weeks. CR, PR and SD are defined as per local review according to RECIST 1.1 (see Section 16.3 Appendix 3 for details). CBR will be evaluated according to RECIST 1.1 (see Section 16.3 Appendix 3 for details).

CBR based on RECIST 1.1 will be calculated based on the FAS and according to the ITT principle. CBR and its two-sided exact binomial 95% confidence interval Clopper CJ and Pearson 1934 will be presented by treatment group.

Time to response (TTR) is defined as the time from the date of randomization to the first documented response of either complete response (CR) or partial response (PR), which must be subsequently confirmed (i.e., the start date of response, not the date when response was confirmed).

TTR will be evaluated according to RECIST 1.1 (see Section 16.3 Appendix 3 for details).

All participants in the FAS will be included in TTR calculations. Participants without a confirmed CR or PR will be censored at the study-maximum follow-up time (i.e., LPLV-FPFV) for participants with a PFS event (i.e., disease progression or death due to any cause), or at the date of the last adequate tumor assessment for participants without a PFS event. TTR will be listed and summarized by treatment group. TTR will be analyzed in the FAS population according to the treatment groups assigned at randomization. The TTR distribution will be estimated using the Kaplan-Meier method, and the Kaplan-Meier curves, medians and 95% confidence intervals of the medians will be presented for each treatment group only if a sufficient number of responses is observed.

Duration of response (DOR) only applies to participants whose best overall response is complete response (CR) or partial response (PR) based on tumor response data per local review. DOR will be evaluated according to RECIST 1.1 (see Section 16.3 Appendix 3 for details).

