16.3.3.2.7 Time to response

Time to overall response (CR or PR) is the time between date of randomization/start of treatment until first documented response (CR or PR). The response may need to be confirmed depending on the type of study and its importance. Where the response needs to be confirmed then time to response is the time to the first CR or PR observed.

Although an analysis on the full population is preferred a descriptive analysis may be performed on the "responders" subset only, in which case the results should be interpreted with caution and in the context of the overall response rates, since the same kind of selection bias may be introduced as described for duration of response in Section 16.3.3.2.5. It is recommended that an analysis of all patients (both responders and non-responders) be performed whether or not a "responders only" descriptive analysis is presented. Where an inferential statistical comparison is required, then all patients should definitely be included in the analysis to ensure the statistical test is valid. For analysis including all patients, patients who did not achieve a response (which may have to be a confirmed response) will be censored using one of the following options.

- at maximum follow-up (i.e. FPFV to LPLV used for the analysis) for patients who had a PFS event (i.e. progressed or died due to any cause). In this case the PFS event is the worst possible outcome as it means the patient cannot subsequently respond. Since the statistical analysis usually makes use of the ranking of times to response it is sufficient to assign the worst possible censoring time which could be observed in the study which is equal to the maximum follow-up time (i.e. time from FPFV to LPLV)
- at last adequate tumor assessment date otherwise. In this case patients have not yet progressed so they theoretically still have a chance of responding

Time to overall complete response (CR) is the time between dates of randomization/start of treatment until first documented CR. Similar analysis considerations including (if appropriate) censoring rules apply for this endpoint described for the time to overall response endpoint.

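### Time to response: non-responders who start a new therapy without a PFS event are censored as if they could still respond, so the Kaplan-Meier curve can end above the ORR

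*SAP*

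**What the plan says.** SAP 2.7.1 runs the TTR clock from randomization: "Time to response (CR or PR) is the time from date of randomization to first documented response of CR or PR", with later confirmation required. All FAS participants are included, and those without a confirmed response are split in two:

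- Those with a PFS event (progression or death from any cause) are censored at "the maximum follow-up time (i.e. FSFV - LSLV used for the analysis) for subjects who had a PFS event". Protocol 12.5.1 agrees; they are "censored at the study-maximum follow-up time (i.e., LPLV-FPFV) for participants with a PFS event".
- Everyone else is censored at "the last adequate tumor assessment date for all other subjects".

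Protocol Appendix 3 (16.3.3.2.7) gives the reasoning. After a PFS event a response is no longer possible. For the others, "In this case patients have not yet progressed so they theoretically still have a chance of responding".

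Four other rules bear on the second group:

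- SAP 2.5.3: "Only tumor assessments performed on or before the start of a new antineoplastic treatment other than study drug(s") count toward BOR, palliative radiotherapy aside. Protocol 12.4.1 and 12.4.3 say the same.
- SAP 2.7.3: a progression or death after new anticancer therapy is censored for PFS. If there is no post-baseline assessment, the censoring date is randomization.
- SAP 2.7.1: clinical deterioration without RECIST evidence is not a progression event.
- SAP 2.5.3: a participant with unknown BOR is a failure for ORR and stays in its denominator.

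SAP 2.7.2 plans Kaplan-Meier TTR curves and medians by arm if there are enough responses, plus a responders-only analysis.

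**The concern.** The split is meant to separate participants who can no longer respond from those who still can. Participants who switch therapy without RECIST progression are on the wrong side of it. They have no PFS event, so they are censored at the last scan, but the BOR rule means that no later scan can give them a countable response or confirm an earlier unconfirmed one. Kaplan-Meier then treats them as having the same chance of a later response as those still under observation, when under the plan's own rules that chance is zero.

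The plan expects such participants. SAP 2.7.2 lists new therapy before progression as a PFS censoring reason, and SAP 2.5.4 lists new therapy before the first post-baseline scan as a reason for unknown BOR. Someone switched for clinical deterioration alone is one example. At stake is a descriptive curve that may suggest a higher share of responders than the ORR in the same report, with the gap growing as more participants switch.

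**Working it through.** **Reference case.** The documents state no TTR figure to reproduce. SAP 5.4.1 works an ORR example with 12 responders of 32. Its posterior is Beta(0.35/0.65 + 12, 21), for which P(ORR ≥ 25%) = 0.9385, matching the stated 0.939. That example is used in the second illustration.

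**Direction.** The curve is 1 − S, where S is the product of (1 − d/n) over response times, d is the number responding and n the number at risk. Taking a non-responder out before a response time lowers n there and raises d/n. So 1 − S cannot fall, and it rises if any response comes later. If every non-responder stays at risk past the last response, the product telescopes to non-responders over total, and 1 − S equals the ORR.

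**First illustration.** Arms 2 and 3 each had 34 participants randomized (protocol, Amendment 4). Assumptions: 12 responders (7 at week 6, 4 at week 12, 1 at week 18), k of the 22 non-responders censored at the week-6 scan after switching, all others at maximum follow-up.

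S = (27/34) × (23 − k)/(27 − k) × (22 − k)/(23 − k) = (27/34) × (22 − k)/(27 − k)

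| k | S | Curve ends at |
|---|---|---|
| 0 | 22/34 = 0.647 | 35.3% (= ORR) |
| 3 | (27/34)(19/24) = 0.629 | 37.1% |
| 6 | (27/34)(16/21) = 0.605 | 39.5% |
| 9 | (27/34)(13/18) = 0.574 | 42.6% |

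**Sensitivity to timing.** With 12 of 32 (ORR 37.5%), responses assumed 6, 4 and 2 at weeks 6, 12 and 18:

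| k | Censored at randomization (no scan) | Week 6 | Week 12 |
|---|---|---|---|
| 1 | 38.7% | 38.2% | 37.8% |
| 3 | 41.4% | 39.9% | 38.5% |
| 5 | 44.4% | 42.0% | 39.3% |
| 8 | 50.0% | 45.8% | 41.1% |

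If instead all 12 responses come at week 6 and the switchers are censored at week 6, the curve ends at 37.5% for every k: no later response, no excess.

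**After the change.** With switchers moved to maximum follow-up and nobody else censored early, both illustrations return to the ORR for every k. If two ongoing non-responders stay censored at week 12 in the 12-of-32 case, S = (26/32)(22/26)(18/20) = 0.619 and the curve ends at 38.1%. Without the change, that case ends at 38.9%, 40.8% or 43.0% for k = 1, 3 or 5.

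**The case against.** The strongest reply is that little depends on this. TTR is descriptive, its Kaplan-Meier display is conditional on enough responses, and no time-point estimates are planned for it. ORR is the declared estimate of the response proportion and the only input to the efficacy rule. In the 34-participant illustration the median is not reached under either rule, and the responders-only summary does not change. All of this stands, but the curve is itself a planned output, and it is the curve that shifts.

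A second reply is that censoring at new therapy is a legitimate choice, follows protocol 12.5.1 and matches the PFS and DOR rule. A reader might therefore infer that the SAP departs from the protocol; it does not. But the plan already keeps participants who cannot respond at risk to maximum follow-up, so leaving switchers out contradicts its own rationale.

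Third, the affected group may be smaller than it looks. The TTR paragraph's gloss on a PFS event, progression or death from any cause, could take in events after the switch, and protocol 8.3.1 asks for scans to continue after new therapy. SAP 2.7.3 points the other way. The text does not settle this.

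Two stronger readings of the wording are tempting. The sentence "The start date is the date of first documented response of CR or PR" might suggest that TTR starts at response. The paragraph's first sentence already starts it at randomization; the later sentence describes the event date and repeats the DOR wording. Likewise, FSFV - LSLV taken as a subtraction is negative, and programmed that way it would drive the 12-of-32 curve to 100%. It is more likely a range, as in Appendix 3, and Appendix 3 (16.3.4.5.1) rules out negative times. Both are wording slips.

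**Conclusion.** The point holds as an inconsistency in a descriptive secondary analysis that should be corrected. The censoring rule can lift the TTR curve above the ORR but cannot push it below. The excess needs at least one response after a switcher's censoring, so a reader should not infer that the curve always ends too high.

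In the 34-participant illustration the excess is 1.8, 4.2 or 7.4 percentage points (37.1, 39.5 and 42.6 less 35.3, from unrounded values). Switch counts, scan timing and response pattern are all assumptions, because the documents do not report how many participants switched without a PFS event. The result also assumes that a confirmed response for TTR follows the BOR exclusion of later scans, which the TTR paragraph does not restate, and that PFS event is read as in SAP 2.7.3.

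Nothing here bears on the primary conclusion. The median is unaffected in the 34-participant scenarios; only the most extreme tabulated case, eight switchers with no scan, brings the curve to 50%.

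**What to change.** In SAP 2.7.1 and protocol 12.5.1 together, censor at maximum follow-up every participant without a confirmed response who had a PFS event or started new anticancer therapy, including those who progress or die after the new therapy. This also settles the ambiguity over PFS event. Keep last-scan censoring for those still evaluable for response. If the protocol is not amended, list the change in SAP section 4, which currently records none.

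Exact agreement with the ORR is not guaranteed, since participants who are ongoing, lost or without scans may still be censored early. A footnote to the curve should say so.

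The primary analysis has already been run (cut-off 27-Feb-2020). Check how TTR was derived there and, if affected, correct or footnote the curve, labelled post hoc.

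Two wording corrections in the SAP TTR paragraph: call the first-response date the event date rather than the start date, and write maximum follow-up as LSLV - FSFV.

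The cost is one derivation condition, using new-therapy dates already needed for BOR and PFS, a few lines of text in two documents and, if needed, a rerun of one output.
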